I will provide copies of the protocol, any subsequent amendments and access to all information furnished by the sponsor to study personnel under my supervision. I will discuss this material with them to ensure that they are fully informed about the investigational study agent and the study protocol. I agree to conduct this clinical trial according to the protocol described herein, except when mutually agreed to in writing with the sponsor. I also agree to conduct this study in compliance with guidelines for Good Pharmacoepidemiology Practices (GPP) as defined by the International Society of Pharmacoepidemiology (ISPE) all applicable national, state, and local regulations, as well as the requirements of the appropriate Institutional Review Board/Independent Ethics Committee (IRB/IEC) and any other institutional requirements.

Principal Investigator:

Signature

Date (dd mmm yy)

Name (please type or print)

Institution

Address (must include country name)

Study Synopsis

Title of the Study: A 5-Year Observational Prospective Registry to Assess Adverse Events of Interest and Effectiveness in Adults with Active, Autoantibody-Positive Systemic Lupus Erythematosus Treated with or without BENLYSTA™ (belimumab)

Clinical Development Phase: 4

Objectives:

Primary Objective

To evaluate the incidence of the following adverse events of special interest (AESI) over 5 years in adults with active autoantibody-positive systemic lupus erythematosus (SLE) who are treated with or without BENLYSTA:

- Malignancies (excluding non-melanoma skin cancers)
- Mortality
- Opportunistic infections and other infections of interest ([Appendix 1](#))
- Non-melanoma skin cancers (NMSC)
- Selected serious psychiatric events ([Appendix 2](#))
- Serious infections

Other Objectives

To evaluate the following effectiveness measures in adults with active autoantibody-positive SLE who are treated with or without BENLYSTA:

- Organ damage as assessed by SLICC/ACR Damage Index ([Appendix 5](#))
- Concomitant SLE medications including steroids
- Hospitalizations

Inclusion Criteria:

Patients enrolled in the registry must meet the following inclusion criteria:

1. Males or females age 18 or older.
2. Have a clinical diagnosis of active SLE.
3. Current or history of autoantibody-positive SLE.
4. Must be treated with SLE therapy including BENLYSTA and/or immunosuppressants (eg, azathioprine, methotrexate, cyclophosphamide, mycophenolate, and biologics).
5. Have the ability to understand the requirements of the study, provide written informed consent, including consent for the use and disclosure of research-related health information, and comply with the study data collection procedures.

Exclusion Criteria:

Patients will be excluded from participating in the registry if they meet any of the following exclusion criteria:

1. Treatment with an investigational drug within one year of enrollment. Investigational drug applies to any drug not approved for sale in the country it is being used.
2. Currently enrolled in a placebo-controlled BENLYSTA (belimumab) clinical trial or a continuation protocol where belimumab is used as an investigational agent.
3. Patients who have a history of BENLYSTA exposure, but are not currently receiving BENLYSTA.
4. Patients only receiving an anti-malarial for SLE.
5. Patients only receiving steroids for SLE.

Study Design:

This is a multi-center, prospective, observational cohort study to evaluate the incidence of adverse events of special interest (AESI) and effectiveness in patients with active, autoantibody-positive SLE treated with and without BENLYSTA. BENLYSTA refers to any commercially available formulation of belimumab. BENLYSTA formulation, intravenous (IV) or subcutaneous (SC), will be recorded for each patient in the protocol database. Patients will receive BENLYSTA at the discretion of their physician. All treatment decisions are at the discretion of the patient and their healthcare provider and are not mandated by study design or protocol. All assessments are intended to be performed at the time of clinical encounters, per routine care. Patients will be enrolled into 1 of 2 cohorts, those who, at baseline, are receiving or initiating BENLYSTA (BENLYSTA cohort) or are not receiving BENLYSTA (comparison cohort). BENLYSTA or comparison cohort patients may be either treatment initiators or current users. Treatment initiators are defined as those patients who have initiated immunosuppressants and/or BENLYSTA in the last 2 months, while the current users are those who have received immunosuppressants and/or BENLYSTA for ≥ 2 months at the time of entry into the registry. The study will enroll approximately 3,000 patients, approximately 2,000 in the BENLYSTA cohort and 1,000 in the comparison cohort. Enrollment is expected to occur primarily in the US, Canada, and Europe. Each patient will be followed for 5 years contributing a total of approximately 7,773 patient years in the BENLYSTA cohort and 3,886 patient years in the comparison cohort, respectively, assuming a 10% annual patient drop-out rate and not accounting for crossover.

Data will be collected at enrollment and at approximately 6 month intervals for 5 years (60 months). All patients will be assessed for AESI including serious infections, opportunistic infections and other infections of interest, malignancies (including NMSC), selected serious psychiatric events and mortality. Organ damage as assessed by SLICC/ACR Damage Index (SDI), concomitant SLE medications including steroids, demography (eg, age, gender, race/ethnicity; where allowed by local regulation), smoking history, alcohol use,

hospitalizations, and disease activity of SLE will also be evaluated in all patients at defined visits (see [Table 6-1](#)). Adverse events not collected in this study should be reported in accordance with the laws and regulations for marketed products in the country in which the event occurred.

Primary Endpoints:

Incidence of the following adverse events of special interest (AESI):

- Malignancies (excluding non-melanoma skin cancers)
- Mortality
- Opportunistic infections and other infections of interest ([Appendix 1](#))
- Non-melanoma skin cancers (NMSC)
- Selected serious psychiatric events ([Appendix 2](#))
- Serious infections

Effectiveness Endpoints:

- Organ damage as assessed by SLICC/ACR Damage Index ([Appendix 5](#))
- Concomitant SLE medications including steroids
- Hospitalizations

Sample Size Consideration:

This registry will enroll approximately 3,000 patients, approximately 2,000 receiving or initiating BENLYSTA plus standard of care (BENLYSTA cohort) and 1,000 standard of care only (comparison cohort). Each patient will be followed for 5 years, contributing a total of approximately 7,773 patient years in the BENLYSTA cohort and 3,886 patient years in the comparison cohort, respectively), assuming a 10% annual patient drop-out rate and not accounting for crossover.

The registry will allow the difference in mortality rate in the BENLYSTA cohort and comparison cohort to be established with a 95% CI of +/-0.32 per 100-subject years, based on an estimated mortality rate of 0.68 per 100-subject years in both treatment groups ([Table 1](#)). The estimated mortality rate was based on the mortality rate in the pooled IV primary safety database in SLE subjects derived from 3 randomized, double-blind, IV placebo-controlled trials, referred to as IV SLE Controlled, Repeat Dose (CRD) studies (ie, integrated database of LBSL02 [placebo-controlled treatment phase only], HGS1006-C1056, and HGS1006-C1057) for all subjects (IV belimumab and placebo) adjusted for subject years. The precision of the rates of the AESI are provided in the table below:

Table 1 Precision of differences in AE rates estimated from a total of 7,773 patient years in the BENLYSTA cohort and 3,886 patient years in the comparison cohort, respectively

Adverse Events	Reference Rate¹ (per 100-patient years)	95% Confidence Interval for difference in AE rates² (per 100-patient years)
All deaths	0.68	±0.32
Serious infection	5.80	±0.93
Opportunistic infection	0.136	±0.14
Malignancy excl. NMSC	0.226	±0.19
NMSC	0.226	±0.19
Selected serious psychiatric events	0.410	±0.25

¹ The reference AE rates were based on the AE rates in the pooled IV primary safety database derived from the IV SLE CRD studies (LBSL02, HGS1006-C1056, HGS1006-C1057) and adjusted for subject years.

² Assuming that the AE rates in BENLYSTA and the control groups were the same as the reference rate.

Analysis of Primary Endpoints:

In addition to analyses that consider initial treatment group (BENLYSTA cohort vs comparison cohort), analyses that specifically account for changes in therapy (in either group) by considering a variety of risk windows will be employed. These analyses will attribute events to BENLYSTA treatment if they occur within the designated risk windows for BENLYSTA exposure and to comparison treatment otherwise. These analyses will allow for a registry patient to contribute person-time to both BENLYSTA treatment, and comparison treatment and as a result, will specifically account for treatment switching to BENLYSTA or from BENLYSTA. Switching between BENLYSTA and comparison treatment will be taken into account in a number of ways in the analysis and will be further defined within the statistical analysis plan. No new analyses for changing between BENLYSTA formulation or stratifying by BENLYSTA formulation are planned. Planned analyses are outlined below; all analyses will be detailed in the statistical analysis plan.

- Analysis by initial treatment group of rate per person years of observation time.
- Analysis by initial treatment group of rate per person years of exposure where BENLYSTA exposure ends 14 weeks (approximately 5 half-lives) after cessation of treatment.
- For serious psychiatric events, BENLYSTA exposure is all time on treatment with BENLYSTA ending 14 weeks (approximately 5 half-lives) after cessation of treatment, with all remaining treatment time attributed to the comparison cohort.
- For serious infections, opportunistic infections and other infections of interest, BENLYSTA exposure is all time on treatment with BENLYSTA ending 6 months after cessation of treatment, with all remaining treatment time attributed to the comparison cohort.
- For NMSC and malignancies excluding NMSC, analysis will be performed where all events will be attributed to BENLYSTA if the patient was ever exposed to BENLYSTA treatment prior to the event and attributed to the comparison cohort otherwise (ie, once exposed, always at risk).
- Mortality will be analyzed applying all the above-mentioned risk windows (eg, 14 weeks, 6 months, and ever-exposed).
- Other risk windows (including risk windows for comparison treatment) may also be assessed and defined in the statistical analysis plan.

Additional safety analysis will be performed comparing BENLYSTA treatment initiators with patients from the comparison cohort that start or switch an immunosuppressant and that have comparable background medication and treatment history. Subgroup analysis will be performed that will include but not be limited to analysis of patients with positive anti-dsDNA and low complement at baseline, patients with SLEDAI 2000 score at baseline (<10 vs ≥ 10), SDI (0 vs ≥ 1), steroid use (yes vs no; ≤ 7.5 mg/day vs >7.5 mg/day), immunosuppressant use (yes vs no; mycophenolate vs immunosuppressant other than mycophenolate), region (US/Canada vs Europe vs other), and race (black race vs other). Safety analyses will be adjusted for potential confounding factors ([Appendix 7](#)) through propensity score methods or other appropriate statistical methods. No new analyses for changing between BENLYSTA formulation or stratifying by BENLYSTA formulation are planned. Further details of the safety analyses will be described in the statistical analysis plan.

Analysis of Effectiveness Endpoints:

For any effectiveness endpoint analyses performed, methods to reduce the potential impact of confounding may be employed. These methods could include subgroup analysis, modeling adjusting for baseline and/or other confounding variables, or patient matching techniques like propensity score analysis. Furthermore, analyses considering changes in BENLYSTA use over time (eg, on or off treatment, but not changes between BENLYSTA formulations) in order to assess BENLYSTA effectiveness, as well as evaluate how these endpoints vary in response to BENLYSTA treatment will be assessed and further explored as appropriate. These analyses will be described in the statistical analysis plan.

Study Calendar:

See [Table 6-1](#) for data collection time points.

Table of Contents

Revision Chronology for HGS1006-C1124 (BEL116543)	2
Milestones	2
Investigator Agreement	3
Study Synopsis	4
Table of Contents	10
List of Tables	12
List of Abbreviations	13
1 Background	15
1.1 Disease Background Relevant to the Registry	15
1.2 BENLYSTA Background Relevant to the Registry	17
1.3 Rationale for the Registry	20
2 Study Design	21
3 Objectives	21

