6.1 Study Enrollment Evaluations

The following data will be collected at enrollment (baseline). Data collection for enrollment may be carried out over more than one clinical evaluation visit.

1. Written informed consent (including consent for the use and disclosure of research-related health information).
2. Demographics (eg, age, gender, race/ethnicity (where allowed by local regulation), smoking history, alcohol use)
3. Medical history (including SLE history). Note: To collect additional important information on potential suicidality-related events, should any of the psychiatric events marked with an asterisk in [Appendix 2](#) be present at enrollment, the investigator should complete the Possible Suicidality-Related History Questionnaire (PSRHQ) eCRF (see [Appendix 3](#)).
4. Potential Confounders for Malignancies and/or Infections List (refer to [Appendix 7](#)).
5. Obtain historical and current SLE medications (immunosuppressants, antimalarials, corticosteroids and biologics). The name of the each SLE medication and start and stop dates will be recorded. In addition, for corticosteroids, the prescribed dose will be recorded. If the patient is receiving BENLYSTA, the date of first dose, and route of administration (IV or SC) will be recorded as well as name of the other SLE medications the patient was receiving at the time BENLYSTA therapy was initiated.
6. SLEDAI 2000 (see [Appendix 6](#)). To complete SLEDAI 2000, data from the following laboratory tests if available: Hematology (WBC, platelets), complement (C3, C4), anti-dsDNA, routine urinalysis, and spot urine for macroscopic/microscopic/proteinuria assessments. Note: Laboratory values should not be attributed on the SLEDAI 2000 unless laboratory values were obtained within 30 days of enrollment otherwise the laboratory values will be noted as not done.
7. SLICC/ACR Damage Index ([Appendix 5](#)).
8. Hospitalizations occurring in the previous 6 months.

9. Confirm patient meets study eligibility criteria.

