## 5.2. Baseline Definition

The protocol specifies Day 0 as baseline, but the Clinical Data Interchange Standards Consortium (CDISC) standard refers to the baseline as Day 1; therefore, baseline date will be referenced as Day 1 in this document. Further information on the definition of study and SLE medication phases is presented in Section 9.5.2.

In general, the baseline value of a variable will be defined as the value of the variable measured at the enrollment visit per eCRF . The exceptions are:

- i. For SLICC, and SLEDAI 2000, measurements done within  $\pm 30$  days of enrollment day will be considered as baseline. If there are multiple records that meet this criteria for the same measurement, the worst-case value will be selected as the baseline value. If the values are equal, the measurement which takes place first will be selected as the baseline value.
- ii. For laboratory, measurements done within  $\pm 30$  days of enrollment day will be considered as baseline. If there are multiple records that meet this criteria for the same measurement, the measurement which takes place first will be selected as the baseline value.
- iii. For SLE medications, a 3-day post enrollment rule is applied such that SLE medications started or initiated between study days 1-4 of enrollment (i.e. Study Day 1, 2, 3 or 4) are counted as baseline medication.
- iv. All hospitalizations (SLE-related and non-SLE-related) which occurred (based on admission date) within 6 months prior to or on the enrollment visit date.

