### 5.6.2. Examination of Subgroups

Descriptive summaries and statistical analyses will be performed separately for the two study cohorts (Current Users and Treatment Initiators).

Study Cohort	Definition / Criteria
Current Users	
 
• Subjects who have received or started qualifying medication(s) for <math>\geq 2</math> months (<math>\geq 62</math> days) prior to enrollment (Day 1)
 

Treatment Initiators	
 
• Subjects who have initiated or started qualifying medication(s) in the last 2 months (<math>< 62</math> days) prior to enrollment into the study (i.e Baseline SLE medication initiation <math>< 62</math> days from study Day 1)
 

*Study cohort can be determined for 'Eligible' subjects only (see section 4)*

For the purpose of study cohort assignment to either a current user or a treatment initiator, the following rules will be used to determine when a subject first received Benlysta and/or Non-Benlysta SLE medications:

- For BENLYSTA subjects: this will be the start date of earliest baseline Benlysta medication.

- For NON-BENLYSTA subjects: this will be the start date of study-qualifying non-benlysta SLE medications or the most recently added immunosuppressant if they are on multiple medications at baseline.

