##### **First step of analysis: Inverse probability of treatment weighting (IPTW)**

Propensity scores will be computed as the probability of being exposed to Benlysta at enrollment given an individual’s baseline characteristics. Logistic regression will be used to derive the PS. Non-stabilized weights (i.e. IPTW) for each individual will be calculated as the inverse of the probability of receiving the actual exposure:  $1/PS$  for the Benlysta arm and  $1/(1-PS)$  for the Non-Benlysta arm.

Inverse probability of treatment weighting (IPTW) (Rosenbaum, 1983) will be used to adjust for differences in covariates balance between exposure groups, Benlysta versus Non-Benlysta. To reduce likelihood of extreme weights being assigned in the analysis, stabilized weights will be computed by multiplying the non-stabilized weight of each individual by the proportion of subjects who were exposed to Benlysta at enrollment :  $p/PS$  for the Benlysta arm and  $(1-p)/(1-PS)$  for the Non-Benlysta arm., (Chesnaye, 2021). For the remainder of the document, references to “weight” refer to stabilized weights.

These weights will create a *pseudopopulation* whereby confounding factors are balanced among Benlysta and non-Benlysta arms. The weights’ distributions will be checked to identify extreme weights which might impact results (see section 7.3.1.3). If the balance assessment reveals that adequate balance cannot be achieved between the Benlysta and non-Benlysta arms (section 7.3.1.2.2), no further analysis using propensity scores will be conducted.

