## 9.9. Appendix 9: Treatment Propensity Score Models Covariates

**Table 4: Treatment Propensity Score Models Covariates**

Variables	Categories/Units	Key covariates*
Year of entry in the study	2013/2014 2015/2016 2017/2018 2019/2020	
Age at baseline	Years	Yes
Sex	Female Male	Yes
BMI	Underweight (<18.5) Normal (18.5 - <25) Overweight (25 - <30) Obese (30 - <40) Extremely obese (>=40)	
Race	Black White Asian Other	Yes
Ethnicity	Hispanic/Latino Not Hispanic/Latino	
Region	US/Canada Europe Other	Yes
Baseline Clinical SLEDAI 2000 score	Score	Yes
Baseline SDI	Score	
SLE duration since diagnosis	Years	
Used corticosteroids for SLE in the past six months	Yes No	Yes
Cardiovascular risk factors	Yes No	
Allergic reactions	Yes No	
Interstitial lung disease	Yes No	
Chronic Obstructive Pulmonary Disease (COPD)	Yes No	
Opportunistic Infection	Yes No	

Variables	Categories/Units	Key covariates*
Any other infection	Yes No	
Autoimmune disorders	Yes No	
Hypogammaglobulinaemia	Yes No	
Cancer	Yes No	
Non-Melanoma Skin Cancer (NMSC)	Yes No	
Family history of cancer	Yes No	
End stage renal failure	Yes No	
Depression and/or anxiety disorder	Yes No	
Suicidal ideation and/or suicidal depression and/or suicidal behavior	Yes No	
Attempted suicide	Yes No	
Dialysis	Yes No	
Transplant	Yes No	
Splenectomy	Yes No	

Treatment propensity score models covariates are collected at baseline.

\* Key covariates will be included in PS models. They are selected based on clinical judgment. If during building the PS model, there is a need to simplify the model specification, retention of key variables will be given priority. Any model simplification involving removal of these key covariates, will require further discussions and alignment with study team prior to implementation.

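### For BENLYSTA current users the propensity covariates are taken at enrollment, after at least two months on drug, so the pooled weighted AESI rates can be biased by an amount and in a direction the documents do not fix

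*Protocol*

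**What the plan says.** Both cohorts may include patients already established on treatment. The Protocol (Synopsis, Study Design; repeated in Section 2) states that "the current users are those who have received immunosuppressants and/or BENLYSTA for ≥ 2 months at the time of entry into the registry". SAP 5.6.2 sets the cut at 62 days before Day 1. For BENLYSTA subjects the date that counts is the first start: "this will be the start date of earliest baseline Benlysta medication". Neither document limits how long before entry that start may be.

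The covariates follow a different clock. SAP 5.2: "In general, the baseline value of a variable will be defined as the value of the variable measured at the enrollment visit per eCRF". SAP 7.3.1: "Propensity scores will be computed as the probability of being exposed to Benlysta at enrollment". The note under Table 4 in SAP 9.9: "Treatment propensity score models covariates are collected at baseline".

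Table 4 lists "Baseline Clinical SLEDAI 2000 score" and steroid use over the past six months, both marked as key covariates. It also lists opportunistic infection, other infection, hypogammaglobulinaemia, cancer, NMSC, depression or anxiety, and suicidality items. None has a rule tying onset to the start of BENLYSTA. Table 4 has no term for current user versus initiator, or for time on drug.

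The model is fitted in the whole evaluable population (SAP 7.3.1). SAP 9.11.4 lists two weighted AESI tables, 54.010 (ITT) and 54.020 (While On Initial Exposure), and neither is split by study cohort.

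**The concern.** A propensity score should balance what was true before the treatment decision. For an initiator, enrollment is close to that moment. For a current user it may be months or years later, and the recorded value may already have been changed by the drug. Weighting then equalises part of the drug's effect along with the confounding.

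The planned checks would not reveal this. The standardized mean differences and variance ratios of SAP 7.3.1.2.2 look good whether the balanced variable precedes or follows exposure. SAP 7.3.1.1.1 treats exchangeability only as a matter of unmeasured confounding.

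The stake is considerable, because 54.010 and 54.020 are the only confounding-adjusted AESI results in the SAP display list, and SAP 7.3.3 labels them primary.

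**Working it through.** **The plan's own scale.** Person-years = N(1 − 0.9^5)/(−ln 0.9). This gives 7,773.5 for N = 2,000 and 3,886.8 for N = 1,000 (stated 7,773 and 3,886). Half-width = 1.96 × √[r(1/7,773 + 1/3,886)]. Serious infection, r = 5.80 per 100 PY: 0.927 (stated 0.93). Deaths, r = 0.68: 0.318 (Table 8-1: 0.32). Both reproduce. The documents give no figure for the bias, so what follows is illustration under stated assumptions.

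**History of infection.** Assumptions: gamma frailty Z with mean 1 and variance v; comparison rate 0.058 per year; T years on treatment before entry, the same in both groups; true rate ratio RR; weighting to the pooled 2:1 history distribution. With cumulative hazard a before entry, P(none) = (1 + av)^(−1/v) and E[Z | none] = 1/(1 + av); E[Z | at least one] follows by subtraction.

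Example with RR 1.5, T = 2, v = 1:
- BENLYSTA: a = 1.5 × 0.058 × 2 = 0.174; P(none) = 0.8518; mean frailty 0.8518 without and 1.8518 with a prior infection.
- Comparison: a = 0.116; P(none) = 0.8961; mean frailty 0.8961 and 1.8961.
- Pooled P(none) = (2 × 0.8518 + 0.8961)/3 = 0.8665.
- Standardised frailty: BENLYSTA 0.8665 × 0.8518 + 0.1335 × 1.8518 = 0.985; comparison 1.030 by the same sum.
- Weighted ratio = 1.5 × 0.9852/1.0295 = 1.436.

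The same formula, among current users only (range over v = 1 to 2):

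| True RR | 2 months | 6 months | 2 years | 5 years |
|---|---|---|---|---|
| 1.14 | 1.14 | 1.13–1.14 | 1.12–1.13 | 1.10–1.11 |
| 1.5 | 1.49 | 1.46–1.48 | 1.39–1.44 | 1.34–1.39 |
| 2.0 | 1.96–1.98 | 1.90–1.95 | 1.75–1.84 | 1.64–1.74 |

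The 1.14 row uses the trial data in Protocol Table 1-1: (48 + 36)/1,347 on belimumab against 37/675 on placebo, 6.24%/5.48% = 1.14.

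**A marker that the drug changes, with initiators diluting.** Suppose the drug acts only through a yes/no marker of prevalence p, multiplies that prevalence by m, and the marker carries infection rate ratio R. The true ratio is [1 + mp(R − 1)]/[1 + p(R − 1)]. If every BENLYSTA patient is a current user, weighting on the recorded marker equalises it and the ratio becomes 1. An exact enumeration of stabilized weighting, with one additional pre-drug confounder, gives:

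| Marker | True | 30% current users | 60% | 90% |
|---|---|---|---|---|
| Doubled, R = 2.5 | 1.10 | 1.07 | 1.04 | 1.01 |
| Tripled, R = 4 | 1.37 | 1.24 | 1.13 | 1.03 |
| Cut by 40%, R = 2 | 0.90 | 0.92 | 0.95 | 0.99 |
| Unaffected | 1.00 | 1.00 | 1.00 | 1.00 |

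The first two rows take p = 5% or 10% by level of the confounder. The formula brackets them: 1.15/1.075 = 1.07 to 1.30/1.15 = 1.13, and 1.45/1.15 = 1.26 to 1.90/1.30 = 1.46. The third row corresponds to p of about 35%: 1.21/1.35 = 0.90.

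A marker raised by the drug hides risk; a marker lowered by it pushes the ratio up. Table 4 may hold both kinds, so the net sign is open. Where the drug does not change the marker there is no bias.

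**The case against.** The case for leaving the plan alone has real content.

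- **Partial contamination.** Much recorded history will predate BENLYSTA. For patients 2 to 6 months on drug, the six-month steroid window includes time before it, and a yes/no item does not move with a dose reduction alone. Initiators dilute what remains. This stands.
- **Comparison current users are also measured on their own therapy.** True, and it means the net distortion is a difference between two on-treatment measurements. It does not cancel the problem.
- **The plan already separates the cohorts.** SAP 7 makes separate presentation the default unless otherwise specified, SAP 9.11.2 lists unweighted initiator tables, and Protocol 8.3.2 promises a comparison of BENLYSTA initiators with comparison patients who start or switch an immunosuppressant. But one propensity model is specified and no initiator-only weighted table is listed, so the gap remains exactly where confounding is adjusted.
- **Re-dating history has its own cost.** An infection on drug before Day 1 may be a genuine predictor when follow-up starts, and discarding it gives up balance on risk. This is why re-dating belongs in a sensitivity analysis.

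Two stronger readings go too far. A reader might infer that a pre-enrollment infection or cancer on drug is the endpoint entered as a covariate; SAP 9.2.1.1 counts events only from enrollment, so it is history. A reader might also infer that the weighted tables will understate infection risk by a definite amount; that needs a time-on-drug distribution, a current-user share and drug effects on each covariate, none of which the documents give.

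**Conclusion.** The structural point holds. As written, the SAP adjusts BENLYSTA current users for values recorded after at least two months of the drug, pools them with initiators, and offers no weighted table free of them. The weighted rates in 54.010 and 54.020 can be biased for that reason.

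Size and direction are unknown. On the frailty assumptions the shift is negligible at 2 to 6 months on drug when the true ratio is near 1.14. It becomes material only with years on drug and a true ratio of 1.5 or more, before dilution by initiators. Those figures also apply a serious-infection rate to history items that are not defined as serious. The conclusion rests on two conditions that the documents neither establish nor exclude: that BENLYSTA changes some Table 4 covariates, and that those covariates predict an AESI.

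Initiators are not wholly exempt. They may be up to 61 days on drug at entry, and SAP 5.2 allows SLEDAI within 30 days either side of enrollment. Their exposure to the problem is bounded, however, and that of current users is not.

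**What to change.** In SAP 7.3 and 9.11.4, fit the propensity model and present the weighted AESI rates separately for Treatment Initiators and Current Users, under both ITT and While On Initial Exposure. Treat the initiator tables as the main confounding-adjusted comparison. Label the current-user and pooled tables as prevalent-user estimates. State that the balance rule in SAP 7.3.1 is applied within each cohort.

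Add two sensitivity analyses for Current Users:

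- **(a)** Where an onset date exists, count a history covariate only if onset precedes the first BENLYSTA dose or, in the NON-BENLYSTA group, the start of the qualifying immunosuppressant. Take steroid use from the dated medication records at that same date. The BENLYSTA anchor is collected (Protocol 6.1): "If the patient is receiving BENLYSTA, the date of first dose, and route of administration (IV or SC) will be recorded".
- **(b)** Show the weighted rates with and without SLEDAI and SDI, which cannot be moved back to the start of treatment.

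The cost is SAP wording and a few extra table runs. Initiator-only intervals will be wider. If 75%, 50% or 25% of each cohort are initiators (assumed), dividing 0.927 by √0.75, √0.50 or √0.25 gives a serious-infection half-width of 1.07, 1.31 or 1.85 per 100 PY; deaths go from 0.32 to 0.37, 0.45 or 0.64. These are unweighted and take no account of variance added by weighting. Some onset dates will be partial or absent: SAP 9.6.2.1 names medical history, but it leaves fully missing dates missing, and the documents do not show an onset date for every Table 4 item. Report how many subjects could not be re-dated.
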